12.2.3 Study Operating Characteristics

Interim Analysis: An interim analysis will be used to test if intervention arm (either during-consultation Prostate Choice or Knowing Your Options pre-consultation DA) has produced better knowledge than the respective control arm. There will be 5 to 6 interim analyses conducted of this type before the final analysis with this plan. The O'Brien-Fleming boundaries⁷⁵ will be

used to determine statistical significance in this interim analysis. If any interim analysis is statistically significant, the DSMB may consider stopping the trial early due to demonstrated efficacy of the intervention arm.

Futility Analysis: This study will also be monitored for early stopping for futility. Repeated confidence interval approach⁷⁶ will be used to test futility. At each interim analysis, a 95% one-sided confidence interval on the difference of knowledge between the intervention and control arm will be computed. If the confidence interval does not cover the target alternative of 0.1 for one of these comparisons, the DSMB may consider stopping the trial early for futility.

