12.2.2 Sample Size and Power Considerations

Sample size and power calculation: We first consider power and sample size under the assumption that patients within the same site are uncorrelated. As this is unlikely to be the case in a group randomized trial, we will discuss the adjustment of the sample size estimate to account for this correlation between patients in the next subsection. A recent Cochrane review suggests that most patients can accurately answer 50% (standard deviation of 12%) of the questions asked of them.⁷⁰ On average, DAs increase that knowledge by 20% to 60% of questions asked being answered correctly, but 95% of trials show absolute knowledge increases of 10% or greater. We will consider an absolute 8% increase in knowledge as a clinically meaningful effect size for either during-consultation Prostate Choice or pre-consultation DA in this clinical trial. Note that the four arms of this study make up a 2 X 2 factorial design. Thus, it is natural to consider evaluating the decision aids using a two-way analysis of variance (ANOVA). In this case, the two factors in the ANOVA will be having received during-consultation Prostate Choice (yes or no) and having received pre-consultation DA (yes or no). We will consider simultaneously testing (at a significance level of 0.025 for each test) the main effects of the two decision aids as our primary analysis. That is, we will simultaneously test the null hypothesis that the average knowledge (i.e. the proportion of correct responses to questions) among those who received the pre-consultation DA is equal to that among those who did not (vs. an alternative that these two averages are not equal), and the null hypothesis that the average knowledge among those who received the during-consultation Prostate Choice is equal to that among those who did not (vs. an alternative that these two averages are not equal). A total sample of 100 patients (25 patients per arm) would give us approximately 85% power to detect a difference between those receiving pre-consultation DA and those not receiving pre-consultation DA, under the alternative that the average knowledge among those receiving pre-consultation DA is 58%, and that the average knowledge among those not receiving pre-consultation DA is 50%, using a two-sample t-test (with two-sided alternative) with a 2.5% significance level (this is equivalent to the F test for the main effects in the ANOVA). Under a similar alternative, the same can be said for the during-consultation Prostate Choice decision aid. Thus, if patients within each site were not correlated with each other, our target sample size would be 100 patients. There will be some, but insufficient power to detect an interaction between the two decision aids, but such effects are rare and not anticipated in this study. Therefore, we will not test for such an interaction in the primary analysis.

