Thus, the denominator of our test statistic should actually be $[(4\sigma^2/n)(1 + (m-1)\rho)]^{(1/2)}$. Therefore, if we replace the original sample size ($n=100$) with $n(1 + (m-1)\rho) = 100*1.4 = 140$ in the denominator of our original test statistic, we will have a test statistic which accounts for the correlation of 0.1 between subjects within each of the 20 sites. Hence, we will target an effective sample size of 140 patients (approximately 35 patients per arm, 7 patients per site). The total sample size may be further inflated by 20% to account for ineligible, cancel and loss to follow-up for longer term secondary outcomes and allow increased power to detect racial/ethnic differences. Therefore, a total number of 172 patients will be enrolled into this clinical trial. These 172 patients, recruited from 20 participating sites (about 9 patients per site) will receive the intervention (or control) to which their location is randomized.

Though we have chosen to power this study based on an absolute meaningful difference of 8%, we determined the necessary sample size for a range of meaningful differences. In each case, the target power was approximately 85% (thought it varied slightly, as we only considered sizes which were divisible by 20, given the number of expected sites) with joint main effect two-sided t-tests with two-sided alternatives at the 2.5% significance level. These sample sizes are as follows (not adjusted for ineligibility, cancel and loss to follow-up):

Meaningful Difference	Total sample size without correlation within sites	Total sample size adjusted for correlation within sites
4%	360	504
6%	180	252
8%	100	140
10%	60	84
12%	40	56

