12.3 Sample Size, Accrual Time, and Study Duration

12.3.1 Patient Population: In order to achieve higher minority accrual (at least 43 AA, and at least 43 AI/AN, and up to 86 White, and/or Asian), we will impose a restriction of at most 50% White and/or Asian participants at each site. Patient accrual will be restricted to AA and AI/AN minority once 50% White or Asian patients are enrolled. We are not oversampling Asian men (n=4) because there are no known disparities in this population. As patient recruitment is not blinded to site in the cluster randomization, we will encourage sites to identify patients prior to randomization and conduct recruitment by an individual independent from the one who delivers the intervention to reduce bias. We will recruit 172 patients (43 per arm).

In addition, in order to prevent imbalance between the arms, sites that over-accrue to the study may be asked to close the study at their institution. Finally, institutions will be given a recruitment goal of at least 2 men who report Hispanic/Latino ethnicity per site, and will be required to hold two slots for Hispanic/Latino participants for the first year of the study in hopes of accruing a similar number of Hispanic/Latino men. These slots will be released after the first year of the study if no Hispanic/Latino participants have been recruited at a given site.

12.3.2 Accrual Rate and Accrual Duration: Based on an estimated accrual rate of 10 patients per month across the 20 participating practices, we expect 1 year to identify and train participating practices, approximately 18 months to enroll patients into the clinical trial and another 18 months to collect follow-up outcomes and perform data cleaning and statistical analysis. The study duration of this clinical trial will be 4 years.

12.3.3 Primary Endpoint Completion Date for ClinicalTrials.gov Reporting: For purposes of ClinicalTrial.gov reporting, the Primary Endpoint Completion Date (PECD) for this study is the time the last patient registered has been followed for at least 12 months.

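### The futility rule uses a 10-point target in a trial powered on 8 points, and a flag on one decision aid puts the whole factorial trial up for stopping

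*Combined protocol and SAP*

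**What the plan says.** Section 12.2.3 (Futility Analysis) names the repeated confidence interval approach and says that at each interim analysis "a 95% one-sided confidence interval on the difference of knowledge between the intervention and control arm will be computed". It then gives the rule: "If the confidence interval does not cover the target alternative of 0.1 for one of these comparisons, the DSMB may consider stopping the trial". The endpoint is the percentage of 12 items answered correctly (section 12.2), so 0.1 is 10 points.

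Section 12.2.2 uses a different value: "We will consider an absolute 8% increase in knowledge as a clinically meaningful effect size", for either aid. In the table of sample sizes there, 8 points is the 140-patient row, which the trial adopts before inflating to 172. Ten points is the 84-patient row. The same section plans on "simultaneously testing (at a significance level of 0.025 for each test) the main effects of the two decision aids as our primary analysis", so the two aids are separate primary hypotheses.

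On the looks, section 12.2.3 says: "There will be 5 to 6 interim analyses conducted of this type before the final analysis with this plan". Section 12.3.2 expects "an estimated accrual rate of 10 patients per month across the 20 participating practices" and "approximately 18 months to enroll patients into the clinical trial". Section 12.6 has DSMB reports, including efficacy, every 6 months.

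**The concern.** There are two faults in the rule and one gap around it.

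- **Target.** An interval that excludes 10 points can still contain 8. The rule can therefore call an aid futile while its data remain compatible with the effect the trial was built to find.
- **Trigger.** One flagged comparison is enough, and what comes up for stopping is the trial. A correct flag on an ineffective aid then endangers the test of an effective one. Changing the target does not remove this.
- **Gap.** Repeated-interval multipliers depend on the number and timing of looks. The plan does not state them, and 5 to 6 looks are not reconciled with the accrual period or the 6-monthly reports.

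At stake is advice to the DSMB to stop for futility when an aid has exactly the design effect, or before a working aid can show its effect.

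**Working it through.** **Inputs from section 12.2.2.** SD 12; design effect 8; two-sided 0.025 per aid; ICC 0.1; 20 sites; 100 patients before clustering, 140 after, 172 enrolled (8.6 per site).

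**The plan's own power.** With 50 against 50 independent patients, SE = 12 × √(2/50) = 2.40, and 8/2.40 − 2.24 = 1.09, which gives 86.3% by the normal approximation and 85.3% by the noncentral t. The stated 85% is reproduced. At 10 points the same sample gives 96.9%, so 0.1 is not the powered alternative.

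**Number of looks.** 172/10 = 17.2 months of accrual. Knowledge is measured straight after the consultation, so 6-monthly reports give 2 looks (months 6 and 12) before the primary data are complete. Stretching accrual to the 2 years in section 13.1 would give 3. The three years in section 1.5 would give 5. I therefore ran 2 to 6 looks.

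**Standard error at a look with m patients per site** (the plan's own variance formula): V = 4 × 144/(20m) × [1 + (m − 1) × 0.1].

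- m = 3 (month 6): V = 11.52, SE = 3.39, information fraction t = 0.51
- m = 6 (month 12): V = 7.20, SE = 2.68, t = 0.82
- m = 8.6 (final): V = 5.89, SE = 2.43

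**Flag rule.** Flag if estimate + multiplier × SE < target. The multipliers are an assumption: c/√t, with joint one-sided 95% cover over all looks including the final one. For 2 looks they are 2.43 and 1.92.

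**Hand check with 2 looks, target 10.** The thresholds are 10 − 2.43 × 3.39 = 1.8 and 10 − 1.92 × 2.68 = 4.8 points.

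- True effect 8: the estimate is below them with probability Φ(−1.84) = 0.033 and Φ(−1.17) = 0.12.
- True effect 0: Φ(0.52) = 0.70 and Φ(1.81) = 0.96.

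With target 8 the four probabilities are 0.008, 0.027, 0.47 and 0.86.

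**Simulation** (300,000 trials per scenario, normal theory, the two estimates independent). Look schedules: m = 3, 6; m = 2.15, 4.3, 6.45; five equally spaced in m; m = 1, 3, 4, 6, 7; m = 1, 2, 4, 5, 6, 7. I re-ran these and the results agree to about one percentage point.

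| Both aids truly 8 | Target 0.1 | Target 0.08 |
|---|---|---|
| Given aid flagged, repeated intervals | 12-16% | 3-4% |
| Either aid flagged, repeated intervals | 23-29% | 6-8% |
| Given aid flagged, plain 1.645 limit | 23-32% | 8-13% |
| Either aid flagged, plain 1.645 limit | 41-54% | 15-24% |

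For ICC 0.05 to 0.2, the per-aid rates are 12-17% against 3-4% (repeated) and 20-35% against 7-14% (plain).

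If an aid's own flag at target 0.1 were always obeyed, its power at ICC 0.1 would fall from 84-85% to 81-82% (repeated) or 68-75% (plain).

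| One aid 8, the other 0; repeated intervals | Target 0.1 | Target 0.08 |
|---|---|---|
| Flag on either aid before the working aid crosses its efficacy bound | 65-73% | 51-59% |
| Working aid's power if any flag always stopped the trial | 27-35% | 40-47% |

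The efficacy bound is O'Brien-Fleming at two-sided 0.025. With futility judged by factor at 0.08, the working aid keeps 84-85% power, essentially the same as with no futility rule.

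**The case against.** The strongest reply is that the target mismatch costs little under the method the plan names. With repeated intervals, obeying an aid's own flag costs about 3 points of power. At 2 looks, 84.9 − 82.2 = 2.7 points are lost against a 12.6% flag rate, and 2.7/12.6 = 21%. So about four-fifths of the flags fall in trials that aid would not have won anyway. This stands. The plain-limit figures are a secondary reading, possible only because the text says no more than 95% one-sided.

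Second, the DSMB is only invited to consider stopping. A board seeing one aid at zero and the other doing well need not stop. This also stands: the 27-35% power is a worst case, not a forecast. But the board works from the written rule, and that rule does not separate the factors.

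Third, the efficacy rule in the same section is likewise worded at trial level. That is a fair remark, and it argues for amending both together.

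Fourth, no section ties the interim analyses to the 6-monthly reports, and 5 or 6 looks in 17.2 months (one every 2.5 to 2.9 months) is possible. The 2 years is a site-selection criterion and the three years a feasibility estimate for one population; neither is the trial's accrual period. The look schedule is thus a gap in specification and would be minor by itself.

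Finally, 0.1 may echo the remark in section 12.2.2 that 95% of decision-aid trials show gains of 10% or more. The plan does not say so, and that remark describes other trials.

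**Conclusion.** The concern holds, as something that should be fixed. The futility target contradicts the design effect, and the one-comparison trigger contradicts the treatment of the two aids as separate primary tests. Under repeated intervals the target raises the chance of flagging a truly effective aid about fourfold (12-16% against 3-4%), with a modest power cost. The trigger matters more: when only one aid works, advice to consider stopping usually arrives before that aid can show its effect, under either target.

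The sizes rest on assumed look times and an assumed O'Brien-Fleming shape for the intervals. The direction does not: at any look and with any multiplier, 0.1 flags at least as readily as 0.08. Because the rule is advisory and concerns futility only, the false-positive rate is not at risk.

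**What to change.** 1. Replace 0.1 with 0.08 in section 12.2.3, or state why 0.1 is used and give its flag rate at a true effect of 8 points.
2. Judge futility by factor, for example: *If the upper repeated confidence limit for an aid is below 0.08, the DSMB may consider that comparison futile; stopping the trial for futility is considered only if both comparisons meet this rule.* Say also what a single flag means for the sites allotted to that aid, and review the trial-level wording of the efficacy rule at the same time.
3. State the repeated-interval multipliers for the looks that will actually be held.
4. Reconcile the 5 to 6 interim analyses with the accrual period and the 6-monthly reports, and set the O'Brien-Fleming boundaries to that schedule.

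The cost is wording, plus somewhat less chance of stopping early for futility. No patients or sites are added.

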12.3 Sample Size, Accrual Time, and Study Duration

12.3.1 Patient Population: In order to achieve higher minority accrual (at least 43 AA, and at least 43 AI/AN, and up to 86 White, and/or Asian), we will impose a restriction of at most 50% White and/or Asian participants at each site. Patient accrual will be restricted to AA and AI/AN minority once 50% White or Asian patients are enrolled. We are not oversampling Asian men (n=4) because there are no known disparities in this population. As patient recruitment is not blinded to site in the cluster randomization, we will encourage sites to identify patients prior to randomization and conduct recruitment by an individual independent from the one who delivers the intervention to reduce bias. We will recruit 172 patients (43 per arm).

In addition, in order to prevent imbalance between the arms, sites that over-accrue to the study may be asked to close the study at their institution. Finally, institutions will be given a recruitment goal of at least 2 men who report Hispanic/Latino ethnicity per site, and will be required to hold two slots for Hispanic/Latino participants for the first year of the study in hopes of accruing a similar number of Hispanic/Latino men. These slots will be released after the first year of the study if no Hispanic/Latino participants have been recruited at a given site.

12.3.2 Accrual Rate and Accrual Duration: Based on an estimated accrual rate of 10 patients per month across the 20 participating practices, we expect 1 year to identify and train participating practices, approximately 18 months to enroll patients into the clinical trial and another 18 months to collect follow-up outcomes and perform data cleaning and statistical analysis. The study duration of this clinical trial will be 4 years.

12.3.3 Primary Endpoint Completion Date for ClinicalTrials.gov Reporting: For purposes of ClinicalTrial.gov reporting, the Primary Endpoint Completion Date (PECD) for this study is the time the last patient registered has been followed for at least 12 months.

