Hence, randomization will be conducted at the participating site level instead of patient level. Participating sites will be randomized to one of the four arms. AA-oriented and AI/AN-oriented practices will be those capable of oversampling two of the three the minority populations we are targeting. Randomization will be designed in such a way that AA-oriented and AI/AN-oriented sites are distributed equally to the four arms of the study to prevent, as much as possible, one minority population from being recruited exclusively in only one or two of the intervention arms.

Recruitment: The greatest limitation to accrual feasibility is identifying AI/AN men with newly diagnosed, localized prostate cancer. National data suggest that conservatively 125 cases of prostate cancer occur annually among self-identified Native American men from the Northern Plains and Alaska.¹⁷ We can identify 80% of those men (N = ~100), and approach 80% of them to participate per year (N = 80). We anticipate conservatively that because our intervention is a non-therapeutic

intervention limited to the office visit, 40% of eligible men at participating sites could enroll (n=40 per year for three years) in the Northern Plains and Alaska combined (this is a conservative estimate—most Mayo Clinic decision aid trials accrue 70% of patients approached). We have access to several urban sites from which to draw African American and Hispanic/Latino men, making their recruitment less difficult. The long term success of this line of research will hinge on decision aids being successfully used and their having a positive impact on patient knowledge and risk-concordant treatment decision making. Because of less geographic clustering, men of Hispanic/Latino ethnicity will be recruited from all study sites with a similar overall accrual target, reserving two slots minimum for them during the first year of accrual.

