4.3 Patient Registration Requirements

- **Informed consent:** the patient must be aware of the neoplastic nature of his/her disease and willingly consent after being informed of the procedure to be followed, the experimental nature of the interventions being tested, alternatives, potential benefits, side-effects, risks, and discomforts. Current human subjects protection committee approval of this protocol and a consent form is required prior to patient consent and registration.
- **Patient completed booklets:** Patient questionnaire booklets are to be ordered prior to the registration of any patients. Patient completed booklets can be ordered by downloading and completing the booklet order form (located under the supplemental documents section of the A191402CD website) and faxing the form to Attn: Operational Support Clerk at [REDACTED]. Samples of the booklets are found in Appendices I and II, which are to be used for reference and IRB submission only. They are not to be used for patient completion.

- **Institutional randomization:** Institutions will be randomized to one of four intervention arms:
 - 1) During- and pre-consultation decision aids
 - 2) Pre-consultation decision aid only
 - 3) During-consultation decision aid only
 - 4) Usual care

The Alliance Statistics and Data Center will randomize institutions once an institution is interested and eligible to participate. All men enrolled at a site will receive the intervention to which the treating institution is randomized.

Specifically, the lead study statistician will randomly assign the initial participating institutions to one of the arms before the study is activated. The randomization will be stratified by center type (i.e. which minority group, if any, the center is “targeting”); so that if for example, there were four initial centers which specialized in Native American/Native Alaskan men, each would be assigned to one of the four arms by randomly selecting one of the four repeatedly without replacement, each time assigning that center to one of the remaining arms. This will be done separately for all center types. For all of these centers, the lead statistician will obtain CTEP Institutional IDs (as well as IDs for affiliates, if any, that may be participating), and will then provide the Alliance randomization center with the initial set of CTEP IDs for each treatment arm.

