Thus, when a patient enrolls at one of the initial participating institutions, the CTEP ID of the center can be checked against the initial randomization list, which will determine which treatment that patient gets (and all patients at that center). In addition, the lead statistician will create a random sequence of arm assignments for additional institutions of each type that join after the study begins, so that whenever a new center joins the study, an arm will already have been determined for that center.

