8.1 Patient identification, scheduling, and consent

Sites should implement standard procedures for identifying eligible patients for this study. Patient eligibility will be determined locally by a combination of chart review and patient self-report. Clinical variables about the patients care germane to eligibility will be ascertained by site staff. Site staff must confirm with the patient that this is not a second opinion, and that this is the first face-to-face visit with the doctor to discuss treatment options. It is not required that patients know their diagnosis before the study is introduced to them.

Prospective patients who are informed about a new diagnosis of prostate cancer will be scheduled to receive a follow-up consultation with a physician to discuss treatment options. The scheduled prostate cancer consultation must be the first consultation after diagnosis (i.e. not a second-opinion or a consultation following previous discussions of treatment options). Physicians may consider referring patients to the study team for recruitment upon receipt of positive PCa biopsy results from the lab if the cancer diagnosis has already been disclosed by telephone or email.

It is critical that the site coordinator identify when this visit is scheduled, and plan to make contact (or arrange for the patient’s physician to make contact) with the prospective participant before their scheduled consultation and inform them about the study. Participating institutions should implement a procedure for alerting the study coordinator when an eligible patient has been scheduled for the initial consultation. Institutional study coordinators will document all contact with all potentially eligible participants and indicate interest/non interest or “not approached.”

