8.2.2 Arms A and B only: Patient interaction with the pre-consultation decision aid

The study coordinator will lead the participant to a designated computer terminal or will provide a tablet with which the participant, in collaboration with a partner, if desired, may interact with the pre-consultation decision aid. Staff will be available for any technical issues that may arise.

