12.2 Statistical Design and Analysis for the Primary Endpoint

Primary Endpoint: The primary outcome, knowledge, will be assessed by a standardized questionnaire (i.e., Prostate Cancer Treatment Questionnaire) administered once, immediately after the clinical consultation while the patient is still at the study site. The number correct from this 12-item measure will be reduced to a percentage of total number correct.

A different method for measuring our primary outcome, knowledge, proposing instead a pre-post approach was considered. However, several factors lead us to favor a one-time post-intervention measurement: 1) Our study's randomized design should control for differences in baseline effects; 2) a pre-post design could be confounded by learning effects associated with the baseline measurement since the baseline and post-intervention measurements would only be 1-2 hours apart. Such learning affects could lead to artificial improvements in our control group which could limit our ability to see "true" differences attributable to the intervention(s); 3) finally, a one-time measurement of knowledge will minimize burden to respondents, particularly during the consenting and baseline measurement period where we seek to impede clinical workflows as little as possible.

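### Identifying patients before randomization (12.3.1) cannot protect against recruitment bias, because each site's arm is fixed before almost all of its patients are diagnosed

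*Combined protocol and SAP*

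**What the plan says.** - **Admission and safeguards (12.3.1).** The sentence opens "As patient recruitment is not blinded to site in the cluster randomization" and then offers two protections, both encouraged and neither required: "we will encourage sites to identify patients prior to randomization and conduct recruitment by an individual independent from the one who delivers the intervention".
- **Unit and timing of randomization.** Section 1.5 states that "randomization will be conducted at the participating site level instead of patient level". Under 4.3, "the lead study statistician will randomly assign the initial participating institutions to one of the arms before the study is activated". For later sites a sequence is drawn in advance, so that "whenever a new center joins the study, an arm will already have been determined for that center". Every man at a site gets that site's arm.
- **Before enrolment (7.2).** Intervention sites choose how to deliver the aids, and staff are trained for the assigned arm, before any patient enters.
- **Patients (3.2, 12.3.2).** Men must be newly diagnosed, with a biopsy in the 4 months before registration and their first consultation still ahead. Enrolment lasts about 18 months.
- **Roles (8.1, 8.2.2).** In 8.1, "It is critical that the site coordinator identify when this visit is scheduled, and plan to make contact", with the patient's physician as an alternative contact. In 8.2.2, "The study coordinator will lead the participant to a designated computer terminal or will provide a tablet".
- **Outcome and analysis (12.2, 12.2.1).** Knowledge is measured once, after the consultation. The first of three reasons for having no pre-test is that "Our study's randomized design should control for differences in baseline effects". Patient covariates in the mixed model are optional.

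**The concern.** In a cluster trial, randomizing sites balances the sites' patient populations in expectation. It does not balance the men who enrol if the decision to approach or to join depends on a known arm. Section 12.3.1 recognises this and relies mainly on identifying patients first. If that step cannot be carried out, the plan has less protection than it claims.

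The primary endpoint is vulnerable because it has no pre-intervention score. A difference in prior knowledge between the men enrolled at aid and non-aid sites would pass straight into the estimated effect, and the plan commits to no patient-level adjustment that could reduce it. One difference in the invitation is written into the protocol: in 8.1, sites with the pre-consultation aid must allow patients additional unhurried time before the visit.

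**Working it through.** **1. Timing.** Set side by side, the sections give this order:

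| Step | When | Section |
|---|---|---|
| Site's arm fixed | Before activation, or pre-drawn before a later site joins | 4.3 |
| Arm-specific training | Before the site's first enrolment | 7.2 |
| Patient's biopsy | At most 4 months before his registration | 3.2.1 |
| Enrolment | 172 patients / 10 per month = 17.2 months, matching the stated 18 or so | 12.3.2 |

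A man can be identified before his site's arm is fixed only if he was diagnosed around the time of assignment and was still awaiting his first consultation when the site opened. That is a small group at the start of accrual.

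**2. Recruiter.** A separate recruiter is feasible. He or she would still know the site's arm, since every man at the site receives it. The procedures also give the study coordinator both the recruitment contact (8.1) and a part in providing Knowing Your Options (8.2.2).

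**3. The plan's own power figure.** Inputs from 12.2.2: difference 8 points, SD 12, two-sided 2.5%, 50 against 50 patients. A two-sample t-test gives 85.3% power (normal approximation 86.3%), against the stated 85% or so. The inputs are confirmed, and no stated power figure is disputed here.

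**4. Illustration for Knowing Your Options.** The documents give no enrolment rates by arm and no link between willingness and knowledge. Assume:

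- 50% of approached men enrol where extra time is asked, and 70% elsewhere;
- willingness and knowledge are jointly normal with correlation r of 0.3 to 0.5.

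Mean knowledge among enrolled men rises by r × SD × φ(z_p)/p, where p is the enrolment rate, φ the standard normal density and z_p the normal quantile of p.

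- φ(z)/p is 0.798 at p = 0.5 and 0.497 at p = 0.7, a difference of 0.301.
- Shift: 0.3 × 12 × 0.301 = 1.08 points; 0.5 × 12 × 0.301 = 1.81 points.
- Against the 8-point target: 1.08/8 = 14%; 1.81/8 = 23%.

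Standard error of a main effect at 140 patients in 20 sites (7 per site, intra-site correlation 0.1):

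- Design effect 1 + 6 × 0.1 = 1.6; SE = 12 × √(4 × 1.6/140) = 2.57 points.

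Rejection probability with no true effect, critical value 2.241:

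- Shift 1.08 (0.42 SE): 3.4% + 0.4% = 3.8%.
- Shift 1.81 (0.70 SE): 6.2% + 0.2% = 6.4%.

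At 172 patients (design effect 1.76, SE 2.43) the figures are 4.0% and 6.9%.

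**5. Sensitivity.** With r = 0.1 and the same enrolment rates, the error at 140 patients is 2.6%. With 60% against 70% and r = 0.3, the shift is 0.5 points and the error 2.8%. If the shift runs against the aid, power falls instead. At 140 patients (normal approximation), power for a true 8-point effect drops from 81% to 67% or 57% for shifts of 1.08 and 1.81.

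**6. Prostate Choice.** With arms lettered as in 8.0, this effect compares A and C with B and D. Knowing Your Options is used in A and B, one on each side. A shift caused by its extra-time request therefore cancels when arms are balanced.

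**The case against.** The plan is not silent. It admits unblinded recruitment, requires a contact log (8.1) and permits covariates (12.2.1). Section 8.1 lets the physician make the contact, and in 8.2.2 the patient works through the aid himself with technical help available, so nothing obliges one person to do both jobs. The pre-test was also dropped because of learning effects over 1 to 2 hours and respondent burden. These points stand. They narrow the concern but do not make the first safeguard workable: no analysis of the log is planned, and the covariates remain optional.

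A reader might infer four stronger things that the documents do not support:

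- **That no patient at all could be identified first.** A few at the start of accrual could be.
- **That the extra-time request biases both main effects.** It cancels from the Prostate Choice contrast in balanced arms. For that aid the exposure is unblinded recruitment in general.
- **That 1.5 supplies arm-specific enrolment of 40% and 70%.** Its 40% is a planning guess for American Indian/Alaska Native men, 40 of about 100 identified. Among the 80 approached it is 40/80 = 50%. The 70% comes from other trials, per patient approached. Mixing the denominators (40% against 70%, r = 0.5) would give 2.8 points and 12.7% error, which is not a like-for-like comparison.
- **That education is not collected.** The Appendix I booklet has no such item, but it has none for race, ethnicity or severity either, and the case report forms are held elsewhere (6.1). Section 1.1 also speaks of a greater effect of education programmes in less educated men, which is effect modification and not evidence about prior knowledge.

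**Conclusion.** The point holds. Identifying patients before randomization is inoperable for almost all patients under 4.3, 7.2 and 3.2. The second safeguard is optional, does not conceal the arm, and sits uneasily with the coordinator's duties. This conclusion rests on the text alone.

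What follows is exposure of the one-time knowledge score to arm-dependent recruitment, not a demonstrated bias. The shift of 1.1 to 1.8 points, and the error of about 4% to 6% against a nominal 2.5%, apply to Knowing Your Options only and depend wholly on the assumed enrolment rates and correlation. Milder assumptions leave the error close to nominal, and the opposite sign costs power. The change should be made because a stated protection does not work and a workable one is cheap.

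**What to change.** - **(a) 12.3.1.** Delete the reference to identifying patients before randomization. Require sites to approach consecutive eligible men, within that section's 50% cap on White and Asian participants and its held Hispanic/Latino slots, using common core invitation wording in all arms.
- **(b) Reporting.** From the contact log already required in 8.1, report approach and enrolment rates by arm.
- **(c) 12.2.1.** Replace optional covariates with pre-specified adjustment for race, ethnicity, disease severity and education level, adding one education item if the case report forms lack it. This is partial control for baseline differences, not a substitute for a pre-test, so the sponsor's learning-effect argument is respected.
- **(d) Roles.** Reconcile 12.3.1 with 8.1 and 8.2.2 on who recruits and who delivers.

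The cost is slightly more site paperwork, possibly one questionnaire item, and a few model degrees of freedom. No extra patients or staff are needed.
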